19. Females of childbearing potential (those who are not surgically sterilized or not postmenopausal for at least 12 months) are excluded from participation in the study if they meet any one of the following conditions:

- they are currently pregnant;
- they plan to become pregnant during the study; and/or
- they are breast-feeding.

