8.3.1 Subject Enrollment

The subject is considered enrolled in the study at the time the IRB/EC approved ICF is signed.

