8.3.4 Subject Discontinuation

A subject MUST be discontinued **prior** to the final study visit for any of the following reasons:

- Change in eligibility prior to treatment

- Voluntary withdrawal
- Death
- Pregnancy
- Lost to follow-up
- Study terminated by Sponsor

Prior to discontinuing a subject, every effort should be made to contact the subject, schedule a final study visit, and obtain as much follow-up data as possible. Adverse events will be followed as described in **Section 12.4.4**. Subject withdrawals will be documented clearly on the source document and applicable CRF.

Notification of subject withdrawals will be made to the Sponsor or their designee through the IRT system and confirmed by the CRO.

Only subjects who are randomized but did not receive study treatment may be replaced. A new subject number will be assigned as long as the total number of treated subjects at the site does not exceed the maximum percentage of the total treated eyes in the study based on the number of active sites as outlined in **Section 7.2**. Subjects who are discontinued from the study following treatment will not be replaced.

Discontinued subjects should be followed outside of the study protocol according to the Investigator's normal standard of care.

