11.1.1 Preoperative Visit: Days -60 to -1

Following identification of a potential subject, the Investigator (or designee) will explain the purpose of the study, procedures, risks/benefits, and subject responsibilities to the potential subject. The subject's willingness and ability to meet the follow-up requirements of the study will be determined. If the subject chooses to participate in the investigation, written informed consent will be obtained. The subject and the person obtaining written consent, will sign and date the IRB/EC approved ICF, at which point the subject is considered part of the study population. The original signed document will be retained in the subject records, and a copy will be provided to the subject. In addition, the applicable privacy regulation requirements must be met.

The subject identification number will be assigned by the site accessing IRT, which will consist of a 2-digit site number (pre-assigned) and a 3-digit chronological order screening number, assigned by IRT and starting with 001 (e.g., 01-001, 01-002; in this example the site number is 01). That subject number will be used to identify the subject throughout the study. It will not be necessary for the surgical procedures to occur in subject number order.

Informed consent must be obtained prior to the Investigator performing study specific procedures that are NOT his/her routine standard of care. After obtaining written informed consent, prospective subjects will be screened to determine whether they meet the entry criteria for the study. Demographic information, medical history, and current medication use will be collected. The preoperative clinical evaluation will be conducted no more than 60 days prior to surgery and will consist of a complete ophthalmic examination including specular microscopy of the central corneal endothelium of the study eye to obtain a baseline central ECD.

Refer to [Appendix A](#) for a schedule of visits and parameters.

11.1.2 Operative Visit: Day 0

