Subjects will be reassessed to reconfirm eligibility. In addition, any changes in concomitant medications, additional medical history since the preoperative study visit, or any adverse events (AEs) will be recorded. If the subject is no longer eligible, he/she will be discontinued from the study. If the subject is eligible, the subject will be randomized via IRT, surgery will be performed and the Investigator will answer questions on source documents concerning the surgery using the surgical procedure described in [Appendix C](#).

Intraoperative surgical staff present during the cataract surgery will confirm their commitment to not mention the treatment assignment in the presence of a subject by signing a masking commitment form prior to the initiation of the cataract surgery. Documentation will be maintained in the site files.

11.1.3 Postoperative Visits (1 through 5): 6 Hours \pm 2 hours to 90 Days \pm 14 days postoperatively

All treated subjects will be seen for five (5) postoperative visits. Refer to [Appendix A](#) for assessments to be performed at these visits.

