12.4.6 Pregnancy

All female subjects of childbearing potential must use an effective method of birth control during the course of the study, in a manner such that risk of contraceptive failure is minimized. Effective contraception is defined as stabilized on oral contraceptive for at least 3 months or use for 3 months of an intrauterine device (IUD), condom with spermicidal, diaphragm with spermicidal, implant, Nuvaring, injection, transdermal patch, and/or abstinence. Females on birth control pills must have taken the same type pill for at least three months prior to entering the study and must not change type during the study. Those who have not used birth control pills in the three months prior to being screened must not begin or resume usage during that period prior to entering the study. Abstinence is allowed as a birth control method.

Before enrolling a female subject of childbearing potential in this clinical trial, the investigator must review the following information about study participation:

- Informed consent requirements; and
- Contraceptives in current use.

Following review of this information and appropriate subject counseling, the investigator or designee and the subject must sign the informed consent before study enrollment.

During the study, all female subjects of childbearing potential are subject to urine pregnancy testing during their study visits and should be instructed to contact the investigator immediately if they suspect they might be pregnant (e.g., missed or late menstrual period).

If a subject or investigator suspects that the subject may be pregnant prior to study enrollment, the study product must be withheld until the results of laboratory pregnancy testing are available. If pregnancy is confirmed, the subject must not receive study product and must not be enrolled in the study.

Subjects who become pregnant during the study will be discontinued from the study and followed until completion of pregnancy. Pregnancy itself is not considered an AE.

All confirmed pregnancies must be immediately reported to the medical monitor and CRO contact within 48 hours of the investigator's awareness of the pregnancy. All confirmed pregnancies must be reported via confirmed facsimile or email transmission and must be submitted on a Pregnancy Report Form within 48 hours of the investigator's awareness of the pregnancy.

13 Statistics

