Appendix A: STUDY FLOW CHART

PROCEDURE/ASSESSMENTS	Preop Visit Day -60 to Day -1	Op Visit Day 0	Postop Visit 1 ^a 6 Hours ± 2 hours Postop	Postop Visit 2 24 Hours ± 4 hours Postop	Postop Visit 3 7 Days ± 2 days Postop	Postop Visit 4 30 Days ± 7 days Postop	Postop Visit 5 90 Days ± 14 days Postop
Informed Consent	X						
Demographic Data	X						
Medical History	X						
Urine Pregnancy Test	X	X ^b			X	X	X
Eligibility Criteria	X	X					
Randomization		X					
Fellow Eye Status	X						
Surgical Procedure ^c		X					
Manifest Subjective Refraction	X						X
Uncorrected Distance VA	X		X	X	X	X	X
Best Corrected Distance VA	X						X
Cataract Classification	X						
Slit Lamp Exam	X		X	X	X	X	X
Intraocular Pressure (Goldmann tonometry)	X		X	X	X	X	X
Fundus Exam (Dilated)	X						X
Ultrasound Pachymetry	X			X			X
ECD via specular microscopy of the central cornea	X						X
Concomitant Medications	X	X	X	X	X	X	X
Adverse Events ^d	X	X	X	X	X	X	X

^a Postoperative Visit 1 must occur on the day of surgery.

^b If last urine pregnancy test was more than 21 days after the preoperative visit, test should be repeated.

^c Required details of the surgical procedure are described in [Appendix C](#).

^d The period of collection of AEs starts from informed consent through study exit

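### Minor, wrong as written: the 21-day repeat rule for the Day 0 pregnancy test (Appendix A, footnote b) counts from the wrong event, so the one scheduled earlier test can never trigger it

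*Combined protocol and SAP*

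**What the plan says.** Appendix A schedules urine pregnancy tests at the preoperative visit, on Day 0 and at Postoperative Visits 3, 4 and 5. Postoperative Visits 1 and 2 are blank. Only the Day 0 entry carries footnote b: "If last urine pregnancy test was more than 21 days after the preoperative visit, test should be repeated".

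On timing, Section 11.1.1 states: "The preoperative clinical evaluation will be conducted no more than 60 days prior to surgery". The interval from that visit to surgery can therefore be 1 to 60 days.

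Several other provisions bear on pregnancy before treatment:

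- Section 8.2, item 19, excludes women of childbearing potential if "they are currently pregnant".
- Section 11.1.2 says of Day 0: "Subjects will be reassessed to reconfirm eligibility". Randomization follows.
- Section 8.3.4 requires discontinuation for "Change in eligibility prior to treatment" and for pregnancy.
- Section 12.4.6 requires contraception and states: "During the study, all female subjects of childbearing potential are subject to urine pregnancy testing during their study visits". It tells women to contact the investigator at once if they suspect pregnancy. It also contains a withholding rule: "If a subject or investigator suspects that the subject may be pregnant prior to study enrollment, the study product must be withheld", until laboratory results are available.

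None of these provisions says how old a negative test may be at surgery.

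**The concern.** The footnote appears to set a freshness limit on the last scheduled pregnancy check before randomization and device exposure. As worded, it measures how long after the preoperative visit the test was done, not how old the test is at surgery. Because the scheduled test is done at that visit, the condition says nothing about its age.

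Sites could then act differently on the same chart. One might treat the Day 0 entry as conditional and find that the condition never applies. Another might test everyone on Day 0. A third might apply the presumed 21-day rule. After Day 0 the next scheduled test is at Postoperative Visit 3, 7 ± 2 days after exposure. A pregnancy found then leads to discontinuation (Sections 8.3.4 and 12.4.6), and Section 8.3.4 does not allow replacement after treatment.

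**Working it through.** No sample size, power or alpha figure is involved. The check enumerates the permitted visit days.

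**Inputs.** The preoperative window is Day -60 to Day -1, which is 60 days (Section 11.1.1, Appendix A). The one scheduled test before Day 0 is done at the preoperative visit (Appendix A). The threshold is more than 21 days (footnote b). Let g be the number of days from the preoperative visit to surgery, so g runs from 1 to 60.

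**Footnote taken literally, Day 0 entry conditional on it.**
- Trigger: (test day − preoperative visit day) > 21.
- The scheduled test gives (−g) − (−g) = 0, and 0 > 21 is false for every g.
- A repeat is triggered on 0 of 60 window days. The footnote alone would let a test up to 60 days old stand.

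**Evident intent: test more than 21 days old at surgery.**
- Trigger: (Day 0 − test day) > 21, that is 0 − (−g) = g > 21.
- This is true for g = 22 to 60, which is 60 − 22 + 1 = 39 of 60 window days (Days -60 to -22).
- No repeat is due for the remaining 21 days (Days -21 to -1). The oldest test that could stand is 21 days old.

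**Day 0 entry taken as unconditional.**
- A test is done on 60 of 60 window days, and the footnote has little purpose.

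**Does an unscheduled test rescue the literal wording?** Take a preoperative visit on Day -40.
- A woman tested only then has a 40-day-old result on Day 0. The literal trigger is 0 > 21, so no repeat is due.
- A woman also tested on Day -10 has a 10-day-old result. The literal trigger is −10 − (−40) = 30 > 21, so a repeat is due.

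The literal rule would repeat the fresher test and accept the older one, the reverse of any plausible purpose.

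These counts are window days, not subjects. The documents give neither the distribution of intervals to surgery nor the number of women of childbearing potential.

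**The case against.** The strongest reply is that the intent is obvious and other text protects the subject. The Day 0 entry itself prompts a test, the Operative Visit is a study visit under Section 12.4.6, and eligibility must be reconfirmed that day against the current-pregnancy exclusion. A site would have to pass over all of this to rely on a 60-day-old result. Much of that stands, and it is why the point is minor. It does not make the footnote correct. The Section 12.4.6 statement on testing cannot mean a test at every visit, because the chart leaves Postoperative Visits 1 and 2 blank. The remaining provisions say what must be true on Day 0, not how recent the supporting test must be.

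Two stronger readings are tempting, and the documents do not support them.

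- A reader might infer that the withholding rule in Section 12.4.6 lapses once consent is signed, because Section 8.3.1 states: "The subject is considered enrolled in the study at the time the IRB/EC approved ICF is signed". But the protocol also uses enrollment for a step after consent. Section 12.4.6 places the consent signature before enrollment, and Appendix B (section 3.0) has some subjects await reading-center confirmation of cell density before being enrolled, which can only follow preoperative imaging. The device is dispensed only on Day 0 (Section 9.1.2), so withholding it before consent would mean little. The rule plausibly covers the interval before surgery, and the instruction to report a suspected pregnancy applies during the study as well.
- A reader might infer that footnote b is the only text governing Day 0 testing. It is the only text that gives a test-age condition, which is a narrower statement.

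**Conclusion.** The footnote is wrong as written, and the point is minor. For the scheduled test its trigger is met on 0 of 60 window days, against 39 of 60 under the evident intent. The literal result follows from the chart alone. The 39 rests on an inference: that the rule was meant to limit the test's age at surgery, and that 21 days is the intended limit. The documents state neither.

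The practical effect is small. It concerns only women aged 45 or over who are neither surgically sterilized nor at least 12 months postmenopausal, and the other safeguards apply to them. Endpoints, power and error rates are unaffected. The documents do not support a conclusion that women would generally be treated without a pregnancy check.

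**What to change.** Change the reference event in footnote b from the preoperative visit to the Operative Visit. Suggested text: *Repeat on Day 0, before randomization, if the most recent urine pregnancy test was done more than 21 days before the Operative Visit.* The sponsor should confirm that 21 days is the intended limit. If the intention was to test every woman of childbearing potential on Day 0, delete the footnote and leave the Day 0 entry unconditional.

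The cost is a one-line change and a few more kits used on Day 0. Section 10.7 already has the CRO supplying urine tests for these subjects.

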Appendix B: METHODS OF CLINICAL EVALUATIONS

Any changes to the procedures described in this Appendix will be provided under separate cover.

1.0 Visual Acuity Testing Methods

Best-corrected visual acuity at Baseline and all scheduled follow-up visits will be measured using the Early Treatment of Diabetic Retinopathy Study (ETDRS) charts at 4 meters.

The charts were designed according to the following principles described by Bailey and Lovie²⁵ and the National Academy of Science-National Research Council (NAS-NRC) Committee on Vision 1980²⁶:

- Letters of equal legibility;
- Combine the letters so that each line is of approximately equal difficulty as described by Ferris et al²⁷;
- Present five letters at each acuity level;
- Space rows by the height of the smaller letter;
- Space letters by the width of same-sized letters; and
- Use a logarithmic progression of letter size from LogMAR (Logarithm of Minimal Angle of Resolution) -0.3 (20/10) to 1.68 (20/957).

This standard describes a single method for the measurement of visual acuity (which is strongly influenced by the methods used in the ETDRS and AREDS protocols) so that measurements obtained using the procedures listed below can be compared within and between sites.²⁷

The subject should attempt to read each letter, line-by-line, left to right, beginning with line 1 at the top of the chart. The subjects should be told that the chart has letters only, no numbers. If the subject reads a number, he or she should be reminded that the chart contains no numbers, and the examiner should then request a letter in lieu of the number. The subject should be asked to read slowly, about one letter per second, so as to achieve the best identification of each letter. He/she is not to proceed to the next letter until he/she has given a definite response.

A maximum effort should be made to identify each letter on the chart. When the subject says he/she cannot read a letter, the subject should be encouraged to guess. If the subject identified two (2) letters (e.g., A or B), the subject should be asked to choose one letter, and, if necessary, to guess. When it becomes evident that no further meaningful readings can be made despite encouragement to read or guess, the examiner should stop the testing for that eye. However, all letters on the last line should be attempted as letter difficulties vary and

the last letter may be the only one read correctly. The number of letters missed or read incorrectly should be noted.

In order to provide standardized and well-controlled assessment of visual acuity, all visual acuity assessments for a subject should be performed consistently (e.g., the same lighting conditions, viewing distance, etc.) at each visit.

Illumination of the ETDRS Chart and Examination Room

The internal illumination of the ETDRS chart should be turned on. This will provide the nominal contrast for each of the charts. Room illumination should be turned off to ensure that the illumination is consistent for each measurement. Ambient sources of light in the room should be kept at a minimum. The room lighting and any ambient sources should be consistent in their use and placement at each subject visit throughout the course of this study.

Manifest Refraction

Each subject must be manually refracted to his/her best correction by an ophthalmologist, optometrist, or a skilled technician using the ETDRS chart at 4 meters with a phoropter or trial frames under photopic lighting conditions. At no time during the study will autorefraction be utilized as a final end point refraction. Autorefractor or lensometer readings may only be utilized to obtain a starting point for the refraction if necessary.

All refractions will be conducted in a manner consistent with the site's standard techniques using 0.25 D steps and utilizing a Jackson cross cylinder method. Manifest refraction is adjusted for optical infinity by subtracting 0.25 D from the sphere of the manifest refraction obtained using the ETDRS chart at 4 meters. The resulting refraction will then be placed in a trial frame and utilized to obtain BCVA results.

Scoring Visual Acuity LogMAR Tests

The examiner records each letter identified correctly by circling the corresponding letter on the Visual Acuity Worksheet. Letters read incorrectly or not read at all are not marked on the form. Each letter read correctly is recorded as one. The total letters read is recorded on the source documents. The LogMAR score will be calculated by the sponsor.

During the course of the study, if the subject is unable to read any letters at 1 meter, they will be asked to count fingers at 0.5 meters (1 foot and 7 5/8 inches). If fingers cannot be counted at 0.5 meters, the vision will be considered hand motion. Hand motion will be determined at 0.5 meters. Light perception will be determined using an indirect ophthalmoscope.

The ETDRS chart must be placed at a distance of 4.00 meters (13 feet and 1.5 inches, or 157.5 inches) from cornea to chart surface, when using a 4-meter chart. For testing at 1 meter, the distance must be 1.00 (39 and 3/8 inches). A measuring tape or meter stick should always be available to verify the chart distance, even if the examining chair is supposed to be immovable or if reference marks are placed on the floor or walls.

The 1-meter distance is measured from the eye of the participant, seated comfortably in a chair with his/her back firmly placed against the chair, to the center of the 2nd or 4th letter of the 3rd line of the chart. The measuring device can be home-made (e.g., a dowel rod accurately cut to a length of 1.00 m) or 1-meter ruler may be purchased.

If it is necessary to refract at the 1-meter distance, remember to add +0.75 sphere to the trial frame. Subtract the +0.75 sphere from the final refraction obtained at the 1-meter distance before recording the refraction.

2.0 SLIT LAMP EXAMINATION

Slit lamp examination will be performed using a slit lamp biomicroscope and observations graded per the following classifications of slit lamp observations:

Cataract Type (pre-operative)

- Nuclear
- Cortical
- Posterior sub-capsular
- Combination

Cataract Density (pre-operative)

- 1+ = Slight
- 2+ = Moderate
- 3+ = Dense
- 4+ = Very dense*

* Very dense cataract excludes subject from study

Central Corneal Stromal Edema (pre-operative and post-operative)

- None – No evidence of central corneal stromal swelling with normal transparency
- Mild – Mild central corneal stromal swelling
- Moderate – Moderate central corneal stromal swelling
- Severe – Definite widespread cloudiness or haziness giving dull ground glass appearance to cornea, or numerous coalescent bullae

Corneal Wound Edema (post-operative only)

- None – No evidence of corneal wound swelling with normal transparency
- Mild – Mild corneal wound swelling
- Moderate – Moderate corneal wound swelling
- Severe – Definite widespread cloudiness or haziness giving dull ground glass appearance to cornea, or numerous coalescent bullae

The slit lamp examination includes the measurement of aqueous cell and flare by the Standardization of Uveitis Nomenclature (SUN) Working Group grading system.⁵ For the evaluation of cells and flare, using a 1 mm x 1 mm slit beam, the following SUN grading scheme must be used:

Anterior Chamber Cells (post-operative)

Grade	Cells in Field
0	<1
0.5+	1-5
1+	6-15
2+	16-25
3+	26-50
4+	>50

Anterior Chamber Flare (post-operative)

Grade	Description
0	None
+1	Faint
+2	Moderate
+3	Marked
+4	Intense

3.0 ECD

Specular microscopes that will be used in the study must first be certified by the central reading center prior to its use for study purposes. At least two study staff members that will be obtaining ECD images and using the specular microscope as delegated by the PI must be trained and certified by the central reading center to ensure proper and consistent imaging prior to capturing study subject images. Documentation of such training and qualifications will be maintained in the site files. The ECD technicians should be delegated as a primary or back-up technician with the primary ECD technician obtaining ECD images whenever possible and the back-up technician obtaining ECD images as necessary in lieu of the primary technician.

Clinical sites are to use their specular microscopes in accordance with the manufacturer's and reading center's recommendations and procedures. Calibration of specular microscopes will be documented and filed at each clinical site.

Standardized ECD count methods²⁸ will be used to minimize variability. The measurement of the ECD in the central cornea will be performed preoperatively and at three months postoperatively (Visit 5) at all sites using a non-contact Specular Microscope (approved by or supplied by the Sponsor). Three images from the central part of the cornea will be obtained for each applicable subject visit.

Initial eligibility determination by the sites is not dependent on receiving reading center ECD results. However, subjects with automated counts below an average of 1750 cells/mm² must await confirmation of >1500 cells/mm² from the reading center prior to enrolling the subject.

To determine ECD, sites will submit all preoperative and three month postoperative images to the reading center (which will be masked) for image analysis. The reading center will determine the mean ECD based on the three images.

